6.3.4 Other Exploratory Endpoints

6.3.4.1 MAP Detection: Blood PCR Assay, Blood Culture Test and Colon Biopsy PCR Assay

Initial blood culture analyses will be performed upon unblinding of the study using data that is available at the time of the data lock. However, subsequent analyses will be performed to allow for further development of the MAP PCR Blood Assay as well as to allow for the 6 month period required to grow MAP in culture for participants whose samples did not had adequate culture growth duration at the time of the data lock. Subsequent analyses will occur when all baseline samples for participants have at least 6 months of duration to grow MAP in culture, next analyses will be repeated when participants with 26 and 52 week data have corresponding 6 and 12 month MAP culture measurements, and finally an analysis will be performed once all participants have their corresponding 6 month MAP culture measurements available. Since this outcome measure is among the exploratory measures and not considered a primary efficacy endpoint, performing analyses at several time points based on the availability of 6-month MAP culture measurements is justified and will not jeopardize the rigor of the statistical testing proposed for the primary and secondary endpoints.

MAP detection analysis is intended to be exploratory. More exploratory analyses may be done but the decision on additional types of analyses will depend on the available data and the final decisions will be made at the time of analysis. Data collected on MAP detection based on PCR Blood Assay, Blood Culture Test and Colon Biopsy PCR assay will be summarized and presented as follows:

- Proportion of subjects (positive/Negative) for MAP at baseline and weeks 26 and week 52 post-baseline will be summarized by treatment group.
- Shift tables summarizing shifts in status (positive to negative; negative to positive, no change) from baseline to week 26 and week 52 post-baseline will be presented by treatment.

The same statistical approach as for the primary analysis will be employed to compare proportion of subjects (positive/negative) for the RHB-104 treated group versus Placebo treated group on

Final Version 3.0, 05 April 2018

ITT population week 26 and week 52 using Cochran-Mantel-Haenszel (CMH) chi-square test controlling for the stratification variable anti-TNF agents use (yes/no).

Additional analysis will be implemented to estimate the correlations between the change from baseline to week 26 and week 52 in PCR Blood Assay level, Blood Culture Test, Colon Biopsy PCR Assay level, and the change from baseline to week 26 and week 52 in the CDAI total score. The results will be presented in graphs including Pearson and Spearman correlation coefficients estimates. Scatter plots of the change in Blood PCR Assay, Blood Culture Test, and Colon Biopsy PCR Assay level versus the change in CDAI total score will be presented.

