1. INTRODUCTION

Crohn's Disease (CD) is an inflammatory bowel disease (IBD) that is serious, debilitating, and potentially life-threatening. The disease is termed a “disease of the young” because it usually strikes children, teens, and young adults. Typically onset is between the ages of 15 to 25 years. Its inflammation can cause severe pain, diarrhea, and other intestinal problems. CD affects men and women equally and appears to show a familial predisposition. Approximately 20-30% of people with CD have a direct blood relative with some form of IBD. World-wide, an estimated 1.4 million people suffer from CD (700,000 US) and the number of sufferers is growing at a rate of at least 1% each year. The disease is now considered to be the second most common chronic inflammatory disorder after rheumatoid arthritis.

One of the potential causes of CD is thought to be gastrointestinal infection with *Mycobacterium avium subspecies paratuberculosis* (MAP) and mycobacterial molecules have been shown to dysregulate immune signaling pathways as part of the organism's evolved survival strategy. MAP has been difficult to isolate from CD patients and it is postulated that it asserts its pathological effect either as an infectious agent or by modifying local cytokine responses.

One of the hindrances to testing for MAP infection in CD patients is that MAP is a very slow growing mycobacterium. MAP shed their cell walls when they infect humans, a tactic that enables them to escape identification and attack by human immune system defenses.

Studies conducted to demonstrate the presence of MAP noted it in 55.4% (range 16-92%) of CD subjects vs. 8.2% (range of 0-49%) of control groups across multiple diagnostic specimens e.g. blood, tissue and culture. Recent work in Israel, Japan, and Ireland has shown that human tissue and white cells can be infected with MAP and this infection results in cytokine production, especially TNF- α and therefore indicates that MAP plays a role in CD.

Current therapies for the treatment of CD aim towards alleviation of the disease symptoms and offer limited efficacy while often causing significant side effects. In addition, the cost of a number of these available therapies is prohibitive, thereby providing limited access to some patients. As a result, there continues to be a significant unmet need for more effective disease management of CD.

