2.1.4 Other Exploratory Efficacy Objectives

1. To characterize the pharmacokinetic profiles of each of the active agents (and active metabolites for clarithromycin and rifabutin) using a population PK approach.
2. To assess the efficacy outcome measures for interaction with the baseline assay results for MAP infection (positive versus negative) to use in development of MAP blood PCR testing.
3. To compare the arm-specific changes in MAP PCR status (positive to negative) from pre- to post-treatment at week 26 and week 52.
4. To compare arm-specific 26-week change from baseline in the endoscopic index (Δ CDEIS and Δ SES-CD) and the clinical index (Δ CDAI)
5. To compare the arm-specific changes in MAP culture status (positive to negative) from pre- to post-treatment at week 26 and week 52.
6. To assess the tissue levels of the active agents of RHB-104 in colon biopsy samples if possible.

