2.2.4 Other Exploratory Efficacy Endpoints/Variable(s)

2.2.4.1 Map Detection Endpoints/Variable

As specified in the objectives, the variables/endpoints in this section are intended to be for exploratory analysis. Depending on the availability of data, specific details of additional exploratory analyses to be conducted will be determined at the time of analyses.

Mycobacterium avium subsp. paratuberculosis (MAP) detection parameters include the following:

- Proportion of subjects with a MAP positive PCR blood assay at baseline.
- Proportion of subjects with a change in MAP blood PCR assay status after week 26 and after week 52 of treatment compared to baseline.
- Proportion of subjects with a MAP positive blood culture at baseline.
- Proportion of subjects with a change in MAP blood culture status after 26 weeks of treatment compared to baseline.
- Proportion of subjects with a change in MAP blood culture status after 52 weeks of treatment compared to baseline.
- Proportion of subjects with MAP positive colon biopsy PCR assay at baseline.
- Proportion of subjects with a change in MAP positive colon biopsy PCR assay status after 26 weeks of treatment compared to baseline.
- Proportion of subjects with a change in MAP positive colon biopsy PCR assay status after 52 weeks

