5. ANALYSIS POPULATIONS

All screened subjects who signed informed consent will be included in the disposition table counts.

The following populations will be used for data analysis.

The Intent-to-Treat (ITT) Population: The primary efficacy analyses will be based on the ITT population, which is defined as all subjects randomized. Subjects will be analyzed according to the treatment group to which they were randomized.

The Modified Intent-to-Treat (mITT) Population: The Modified Intent-to-treat population is defined as patients who fulfill all inclusion/exclusion criteria. The sensitivity analyses will be performed using the mITT population. Subjects will be analyzed according to the treatment group to which they were randomized.

The Safety Population (SAF): The safety population includes subjects who are randomized and receive at least one dose of study medication. The primary safety analyses will be based on the SAF population. Subjects will be analyzed according to the treatment which they actually received.

Per-Protocol Population (PP): The PP Population includes all randomized subjects who receive at least one dose of RHB-104 or placebo and complete dose escalation to target dose of 5 capsules bid, as well as all subjects without major protocol deviations that would have a significant impact on clinical outcome. Relevant protocol deviations may include errors in treatment assignment, the use of excluded medication that might affect study drug bioavailability, poor compliance (< 80% compliant over study duration), and subjects lost to follow-up. Protocol deviations will be reviewed and the list of major deviations warranting exclusion from the PP Population will be finalized prior to study unblinding. Subjects will be analyzed according to the treatment group to which they were randomized.

The primary and key secondary efficacy sensitivity analyses may be repeated on the PP Population.

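### The MAP objective is positive-to-negative conversion, but the endpoint counts any change and the only between-arm test compares positivity in all ITT subjects, so no specified test addresses it (minor, exploratory)

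*SAP*

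**What the plan says.** **Objective.** SAP 2.1.4 lists as objective 3 "To compare the arm-specific changes in MAP PCR status (positive to negative) from pre- to post-treatment at week 26 and week 52" and as objective 5 "To compare the arm-specific changes in MAP culture status (positive to negative) from pre- to post-treatment at week 26 and week 52". The protocol synopsis has the same aims as exploratory objectives 11 and 13.

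**Endpoint.** SAP 2.2.4.1 lists, for blood PCR, "Proportion of subjects with a change in MAP blood PCR assay status after week 26 and after week 52 of treatment compared to baseline" and, for blood culture, "Proportion of subjects with a change in MAP blood culture status after 26 weeks of treatment compared to baseline", with a matching culture item for Week 52. The protocol's outcome measures are worded in the same way. No direction is given, and the denominator is not limited to subjects positive at baseline.

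**Test.** SAP 6.3.4.1 gives a single between-arm test: "The same statistical approach as for the primary analysis will be employed to compare proportion of subjects (positive/negative"), for RHB-104 against placebo, in the "ITT population week 26 and week 52 using Cochran-Mantel-Haenszel (CMH) chi-square test controlling for the stratification variable anti-TNF agents use (yes/no"). SAP 5 gives the ITT population as one "which is defined as all subjects randomized", whatever their baseline MAP status.

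**Descriptive output.** SAP 6.3.4.1 also plans shift tables by treatment that separate positive-to-negative from negative-to-positive (Tables 14.2.4.2.1 to 14.2.4.2.3). No test or interval is attached to them.

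**The concern.** Three different quantities stand where there should be one. The objective is clearance in subjects who had MAP to clear. The endpoint gives the same credit to clearing MAP and to newly testing positive. The test compares how many subjects are positive at a visit, regardless of where they started.

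A subject who tests negative at baseline cannot convert from positive to negative. Such subjects add nothing to the clearance contrast but remain in the denominator of the test. The only adjustment is for anti-TNF use. By contrast, the SAP's change analyses for SF-36, IBDQ, CRP, calprotectin and endoscopy all adjust for the baseline value.

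At stake is how well the trial can answer its own exploratory question about anti-MAP activity, which is the rationale for the combination. Further MAP analyses are left to the time of analysis, so a clearance test added later would be chosen with the data in hand.

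**Working it through.** The plan states no power, rate or sample size for the MAP comparison, so there is no figure of its own to reproduce. What follows is an illustration.

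**Could the test already be a conversion test?** The first bullet of the data presentation in SAP 6.3.4.1 uses the same positive/negative wording for the proportion at baseline and at Weeks 26 and 52. The tested quantity is therefore positivity at a visit. The correlations that follow relate MAP measures to CDAI, and the logistic models in SAP 6.3.1 have remission as the outcome. Neither compares clearance between arms.

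**Inputs**
- From the documents: 162 per arm (SAP 6.1.9); two-sided 0.05, used as a nominal level (SAP 6.1.1); baseline positivity *b*, for which the SAP introduction cites studies that "noted it in 55.4% (range 16-92%) of CD subjects". That is a literature figure across specimen types, used here only as a range. The 30% row is an added intermediate value.
- Assumed: clearance *c* = 60% RHB-104 vs 30% placebo; new positivity *g* = 10% in both arms; complete data; strata ignored.

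**Formulas**
- Positivity at follow-up = *b*(1 − *c*) + (1 − *b*)*g*
- Any change = *bc* + (1 − *b*)*g*
- Conversion among baseline positives = *c*, with 162 × *b* subjects per arm
- Power = Φ[(|p₁ − p₂| − 1.96·SE₀)/SE₁], with SE₀ pooled and SE₁ unpooled

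With equal *g*, the (1 − *b*)*g* terms cancel. The positivity difference is then *b* times the clearance difference, here *b* × 30 points.

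**Dilution**

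| *b* | Positivity, RHB-104 vs placebo | Difference (points) | Power, planned ITT test | Baseline positives per arm | Power, conversion test |
|---|---|---|---|---|---|
| 16% | 14.8% vs 19.6% | 4.8 | 21% | about 26 | 59% |
| 30% | 19.0% vs 28.0% | 9.0 | 48% | about 49 | 86% |
| 55.4% | 26.6% vs 43.2% | 16.6 | 88% | about 90 | 99% |
| 92% | 37.6% vs 65.2% | 27.6 | >99% | about 149 | >99% |

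For example, at *b* = 30%: 0.30 × 0.40 + 0.70 × 0.10 = 19.0%, and 0.30 × 0.70 + 0.70 × 0.10 = 28.0%.

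A smaller assumed effect (50% vs 30%, no new positivity) gives the same pattern: 16% vs 31% at *b* = 16%, 56% vs 79% at 55.4%, and 92% vs 94% at 92%.

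**Unequal new positivity** (*b* = 30%, clearance 60% vs 30%)
- New positivity 0% vs 13%: any change is 0.30 × 0.60 = 18.0% vs 0.30 × 0.30 + 0.70 × 0.13 = 18.1%, so clearance is hidden. The positivity test, however, compares 0.30 × 0.40 = 12.0% with 0.30 × 0.70 + 0.70 × 0.13 = 30.1%, with about 98% power.
- New positivity 13% vs 0%: positivity is 0.12 + 0.091 = 21.1% vs 21.0%, so clearance is hidden there. Any change is 0.18 + 0.091 = 27.1% vs 9.0%.

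In general, write Δ*c* and Δ*g* for the differences between arms. Any change is null only if *b*Δ*c* = −(1 − *b*)Δ*g*. Positivity is null only if *b*Δ*c* = +(1 − *b*)Δ*g*. Both can hold only if Δ*c* = 0.

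**The case against.** The best defence is that clearance by arm is already planned. The shift tables report positive-to-negative counts by treatment at Weeks 26 and 52, and the objective says to compare, not to test formally. The section is exploratory, p-values outside the hierarchy are nominal (SAP 6.1.2), and further analyses are expressly allowed. The ITT positivity test is a valid randomized comparison of a different quantity. It also keeps subjects whose baseline assay was falsely negative, a real possibility given the SAP introduction's account of how hard MAP is to detect. All of this stands, and it limits the weight of the point. It does not supply a pre-specified between-arm test of the stated objective.

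The size also depends on assumed rates. At the SAP's overall 55.4% the loss is moderate, and at 92% it is negligible. The figures apply to blood PCR at most, because SAP 3 limits culture to North American sites and colonoscopy to consenting subjects, with biopsies optional.

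Two stronger readings are tempting, and the documents support neither:
- A reader might infer that a real clearance effect could cancel to nothing in both the any-change endpoint and the positivity test. The algebra rules that out. What can weaken both together is dilution: at *b* = 16% with 10% new positivity in each arm, power is about 22% for any change and 21% for positivity.
- A reader might infer that a null result would misdirect development of the blood PCR test. The objective tied to that development is the interaction of efficacy with baseline MAP status (SAP 2.1.4, objective 2), not the conversion objectives. The documents also call MAP a potential cause of Crohn's disease, not an established one.

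**Conclusion.** The mismatch between objective, endpoint and test is real and visible in the text. No specified test addresses positive-to-negative conversion, which is shown only descriptively. When new positivity is equal between arms, the ITT comparison shrinks the clearance difference by the factor *b*. Under the assumptions above, the cost is 38 points of power at 16% or 30% baseline positivity (59 − 21; 86 − 48), 11 points at 55.4% (99 − 88), and practically none at 92%. Unequal new positivity can mask clearance in one of the two measures but not fully in both, and it can also enlarge the positivity difference.

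The clearance and new-positivity rates are assumptions, and SAP 6.3.4.1 does not say how a missing MAP result is counted. This is a minor, exploratory issue. It touches neither the primary endpoint nor the key secondary hierarchy, and no confirmatory conclusion depends on it.

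**What to change.** - In SAP 2.2.4.1, replace the undirected change items with two endpoints: positive-to-negative among subjects positive at baseline, and negative-to-positive among subjects negative at baseline.
- In SAP 6.3.4.1, add the CMH test stratified by anti-TNF use, with a nominal p-value, for positive-to-negative conversion in subjects positive at baseline by the same assay.
- Keep the ITT positivity comparison and label it supplementary. Keep the shift tables as planned.

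The cost is a few lines of SAP text, with the same data and the same test. Baseline MAP status is sampled at the baseline visit, so the restriction keeps a randomized comparison within baseline positives. The downsides are a smaller test set (about 26 per arm if only 16% are positive) and the exclusion of subjects with a false-negative baseline assay, which is why the ITT comparison should stay alongside.

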6.3.4.2 Drug Levels in Tissue Samples

This is an exploratory analysis and will depend on the samples available at the end of the study for analysis. The tissue samples being collected will be analyzed for drug levels if possible at the end of the study. The patient listings will be presented with correlation of drug levels with CDAI and the other efficacy parameters assessed.

6.4 Population PK Analysis

Population PK analysis will be detailed in a separate document.

6.5 Safety Analysis

All summarization of safety data will be based on the safety population.

6.5.1 Adverse Events

Each verbatim adverse event (AE) term recorded during the study will be mapped to a system organ class and preferred term using the current MedDRA Dictionary.

A treatment-emergent AE (TEAE) is defined as an AE that based on start date information occurred after the first study drug administration or an AE that started before the first study drug administration but worsened in severity (i.e., became more severe) after administration of the study drug.

Treatment related adverse events will be defined as the adverse events for which the investigator indicates the relationship to study drug as possible, probable, or definite. If the relationship to study drug for an AE is not recorded, it will be assumed to be treatment related in the summary tables. Similarly, if severity of an AE is missing, the severity will be summarized as severe.

A by-subject listing of all AEs (including non-treatment-emergent AEs) will be provided and will include all AE data recorded on the eCRF. All summaries of AEs will present the number and percent of subjects reported events by system organ class and preferred term and by treatment group. If a subject has multiple occurrences of an AE, the subject will be counted only once in the respective AE.

For summaries of adverse events by maximum severity or maximum relationship, if a subject has multiple occurrences of an AE, the subject will be counted only once for the respective Preferred Term at the maximum severity or maximum relationship.

An overall summary table by treatment and overall of AEs, SAEs, TEAEs, Serious TEAEs, treatment-related TEAEs, treatment-related SAEs, TEAEs leading to study discontinuation and study deaths will be provided using number and % of subjects.

Summary tables by treatment and overall will be provided by SOC and preferred term for each of the following types of AEs:

- All Treatment emergent AEs
- Study Drug related treatment emergent AEs
- Treatment emergent AEs by maximum severity
- Treatment emergent AEs leading to study discontinuation
- Serious Treatment emergent AEs (SAEs)
- Treatment-related serious AEs
- Treatment emergent AEs leading to Death

The following listings will be provided:

- All AEs
- Treatment related AEs
- AEs leading to study discontinuation
- SAEs
- Deaths

All study deaths will be listed using date and cause of death along with autopsy results as entered on the Death CRF.

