	 Change in dose or discontinuation of oral 5-aminosalicylic acid (5-ASA) compounds less than 4 weeks prior to baseline. 				
	 Change in dose or discontinuation of corticosteroids less than 2 weeks prior to baseline. 				
	 Change in dose or discontinuation of azathioprine, 6-mercaptopurine (6-MP) or methotrexate less than 8 weeks prior to baseline. 				
	 Change in dose or discontinuation of infliximab or adalimumab less than 14 weeks prior to baseline. 				
	 Treatment with vedolizumab less than 120 days prior to baseline or biological therapies (apart from infliximab or adalimumab) less than 60 days prior to baseline. 				
	Previous treatment with rifabutin and/or clofazimine.				
	 Oral or parenteral antibiotics in the 4 weeks prior to baseline (topical antibiotics are permitted). 				
	 Treatment with probiotics (excluding yogurt and yogurt-derived products) in the 4 weeks prior to baseline. 				
	Females who have a positive pregnancy test or are lactating.				
Number of Subjects:	Estimated total: 410 subjects, curtailed to 324 with Protocol Version 11.0, will be randomized into the study.				
Number of Sites:	The study will be conducted at up to 150 sites in the USA, Canada, Israel, Australia, New Zealand, Poland, Bulgaria, Czech Republic, Romania, Slovakia and Serbia.				
Study Design:	This study is a multicenter, Phase III, randomized, placebo-controlled, double-blind study designed to evaluate the efficacy and safety of RHB-104 compared to placebo to treat subjects with moderate to severe CD. RHB-104 consists of 3 antibiotics with activity against Mycobacterium avium subsp. paratuberculosis (MAP), a potential cause of CD. Subjects with active CD will be randomized at baseline in a 1:1 fashion to receive up to 52 weeks of RHB-104 or placebo. Randomization will be performed within strata defined by whether subjects use protocol permitted anti-TNF agents (yes or no). Subjects will remain on stable doses of their baseline CD treatment although steroids may be tapered after Week 8 at the discretion of the investigator.				

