	The study is designed to assess remission at Week 26 as the primary endpoint. However, as MAP are slow growing mycobacteria without a proven antibiotic treatment, the duration of antibiotic treatment needed to achieve remission in subjects with CD caused by MAP may be longer than 26 weeks. Subjects with response at week 26 may ultimately achieve remission at a later time point with continued treatment for MAP. Also, subjects with CD treated for underlying MAP infection may experience benefits with a longer period of time in response or remission with RHB-104 treatment compared to placebo. Thus, the study is also designed to assess response, remission, and maintenance of remission in subjects on randomized treatment through week 52.				

	Blood samples will be collected at baseline and at every visit after the initial 4 weeks of treatment to test for MAP in the serum using a polymerase chain reaction (PCR) assay MAP cultures will be prepared from whole blood collected at the baseline visit and after 26 and 52 weeks of treatment.						
	Safety and pharmacokinetics of the fixed-dose combination product, RHB-104, will also be assessed.						
	Colonoscopy will be done in consenting subjects prior to initiation of study drug and after 26 weeks of study drug to assess for mucosal healing as well as MAP status via PCR and culture. Optional biopsies will also be collected for possible measurement of tissue drug levels and archived for future MAP determinations.						
	Study Visit Schedule:						
	Screening, baseline, and follow-up visits at weeks 2, 4, 6 (+/- 3 days), 8, 12, 16, 20, 26, 35, 44, 52, and 56 (+/- 7 days). Subjects undergoing colonoscopy will have a procedural visit after week 26 assessment so as to not interfere with data collection.						
Subject Participation Duration:	Subjects are expected to participate up to 62 weeks. However, subjects who complete 26 weeks of study drug administration and remain out of remission e.g. CDAI ≥150, will be eligible for open label treatment with RHB-104 in an extension study (protocol RHB-104-04). Subjects may elect to continue in the RHB-104-01 study, and will remain in the RHB-104-01 study until study drug administration in the RHB-104-04, if applicable.						
Treatment:	RHB-104; a fixed-dose combination of 95 mg clarithromycin, 45 mg rifabutin, and 10 mg clofazimine. Placebo is a capsule with a similar appearance as RHB-104.						
Route of Administration:	Oral capsule.						

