Dosage Regimen for Investigational Product:	The target dose of RHB-104 will be 5 capsules administered bid. In order to reach this target with minimal adverse effects, the subject's dose will titrated up over the first 4 weeks of treatment, and the dose will remain stable thereaft (see schedule below). Subjects randomized to placebo will receive the same number capsules as the RHB-104 group according to the schedule below. The study drug vibe taken with food. Subjects who fail dose escalation to 5 capsules bid will be considered treatment failures and withdrawn from the study.						
	Dose Titration by Week for initiating RHB-104						
	Week	1	2	3	4	5-52	
	Study Drug	1 capsule bid	2 capsules bid	3 capsules bid	4 capsules bid	5 capsules bid	
Outcome Measures			me measure) -	- Remission in	a subject is def	fined as a CDAI	
	 Response – A response in the individual subject is defined as reduction in CDAI score of ≥100 from baseline. Time to remission – The time (weeks after randomization) that a subject first records a state of remission. Duration of remission – The time that a subject is in a state of remission. Time to response – The time (weeks after randomization) that a subject first achieves a state of response. 						
	Duration of response – The time that a subject is in a state of response.						
	Maintenance	of Remission	- Remission	in a subject fro	m week 26 thr	ough week 52.	

Other Outcome Measures

MAP Detection:

- Proportion of randomized subjects with a MAP positive blood PCR assay at baseline
- Proportion of subjects with a change in MAP blood PCR assay status after 26 weeks of treatment compared to baseline
- Proportion of subjects with a change in MAP blood PCR assay status after 52 weeks of treatment compared to baseline
- Sequential comparison of MAP blood PCR assay results per subject
- Proportion of randomized subjects with a MAP positive blood culture at baseline
- Proportion of subjects with a change in MAP blood culture status after 26 weeks of treatment compared to baseline
- Proportion of subjects with a change in MAP blood culture status after 52 weeks of treatment compared to baseline
- Proportion of randomized subjects with a MAP positive colon biopsy PCR assay at baseline
- Proportion of subjects with a change in MAP positive colon biopsy PCR assay status after 26 weeks of treatment compared to baseline
- Proportion of randomized subjects with a MAP positive colon biopsy culture at baseline

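### Adverse events are compared only as crude whole-study percentages, although Week 26 non-remitters, assumed to be more frequent on placebo, may leave for open-label drug, so follow-up can differ by arm

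*SAP*

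**What the plan says.** **How adverse events are summarised.** SAP 6.5.1 specifies one type of measure: "All summaries of AEs will present the number and percent of subjects reported events by system organ class and preferred term", by treatment group. The overall table of AEs, SAEs and "study deaths will be provided using number and % of subjects". A subject with several occurrences of an AE counts once. The titles of Tables 14.3.1.1 to 14.3.1.7 carry no time cut and no person-time. A treatment-emergent AE is one that "occurred after the first study drug administration" or that worsened after it. No end of the window is stated.

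**How long subjects are observed.** Under the protocol synopsis, subjects are "randomized at baseline in a 1:1 fashion to receive up to 52 weeks of RHB-104 or placebo", with "follow-up visits at weeks 2, 4, 6 (+/- 3 days), 8, 12, 16, 20, 26, 35, 44, 52, and 56". Two rules can shorten this:

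- Subject Participation Duration: "subjects who complete 26 weeks of study drug administration and remain out of remission e.g. CDAI ≥150, will be eligible for open label treatment" in RHB-104-04. Subjects may instead stay in this trial. Those who transfer remain in it until they take study drug in RHB-104-04.
- Dosage Regimen: "Subjects who fail dose escalation to 5 capsules bid will be considered treatment failures and withdrawn from the study".

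The SAP text does not mention RHB-104-04. SAP 6.2.1 summarises completion of Weeks 26 and 52 and reasons for discontinuation by arm, and SAP 6.2.4.1 summarises time on treatment by arm. Neither is linked to the AE tables.

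**The concern.** Whether a subject may leave after Week 26 depends on remission, which is what the drug is meant to change. Randomisation therefore does not balance follow-up after that point. In a crude percentage, a subject seen for 26 weeks and one seen for 56 weeks weigh the same in the denominator. If more placebo subjects leave, fewer of their later events can be recorded, and RHB-104 looks worse than it is for events that arise late.

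The by-arm AE, SAE and discontinuation tables are the main evidence for the safety objective (SAP 2.1.5). With treatment planned for up to 52 weeks, the period after Week 26 matters.

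**Working it through.** **1. Source of the remission rates.** The documents give no AE follow-up by arm. The relevant design figure is the sample size for 21% vs 36% remission (protocol, Statistical Considerations; SAP 6.1.9). The usual two-proportion formula with 90% power and two-sided alpha 0.049 gives 190 per group, or 203 with continuity correction, against 205 stated. At 162 per group the power is 85.0%, consistent with the stated minimum of 80%. The design rates are therefore used consistently.

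**2. Share that could be eligible.** RHB-104: 1 − 0.36 = 0.64. Placebo: 1 − 0.21 = 0.79. Both are ceilings. Subjects with a missing Week 26 assessment, and subjects counted as failures because of rescue (SAP 2.2.1 and 6.1.8), are included in non-remission. Dropouts before Week 26 have not completed 26 weeks of drug, and a rescued subject may have a CDAI below 150.

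**3. Assumptions for the illustration.**
- A share f of non-remitters transfers, equal in both arms. The documents do not give f, so 0 to 1 is shown.
- Follow-up is 26 weeks for transfers and 56 weeks for everyone else.
- The true event rate is constant and the same in both arms: 0.5 or 1.0 per year.

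**4. Formulas.** The risk of a first event by week t is I(t) = 1 − exp(−rate × t/52). If a share s leaves at Week 26, the crude percentage is s × I(26) + (1 − s) × I(56). The false difference is f × (0.79 − 0.64) × [I(56) − I(26)].

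- Rate 0.5: I(26) = 22.1%, I(56) = 41.6%. At f = 1 the difference is 0.15 × 19.5 = 2.9 points.
- Rate 1.0: I(26) = 39.3%, I(56) = 65.9%. At f = 1 the difference is 0.15 × 26.6 = 4.0 points.

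**5. Results, RHB-104 vs placebo.**

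| f | Leave at Week 26 | Mean weeks observed | Crude %, rate 0.5 | Crude %, rate 1.0 |
|---|---|---|---|---|
| 0 | 0% vs 0% | 56.0 vs 56.0 | equal | equal |
| 0.5 | 32.0% vs 39.5% | 46.4 vs 44.2 | 35.4 vs 33.9 (+1.5) | 57.4 vs 55.4 (+2.0) |
| 1 | 64% vs 79% | 36.8 vs 32.3 | 29.1 vs 26.2 (+2.9) | 48.9 vs 44.9 (+4.0) |

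The mean weeks at f = 1 are 0.64 × 26 + 0.36 × 56 = 36.8 and 0.79 × 26 + 0.21 × 56 = 32.3.

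**6. Sensitivity.** If observation stops at Week 52 rather than 56, mean follow-up at f = 1 is 35.4 vs 31.5 weeks. Events with a 52-week risk of 10%, 30% or 60% then show a false excess of 0.7, 2.1 or 3.5 points, and 0.4, 1.0 or 1.7 at f = 0.5. If RHB-104 remission were 30% instead of 36% (an assumption), the figures at f = 1 fall to 0.4, 1.2 and 2.1 points. The effect vanishes if RHB-104 non-remitters transfer 0.79/0.64 = 1.23 times as often as placebo non-remitters.

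**7. Early withdrawal.** Suppose, for illustration, that early leavers exit at Week 8 and count as non-remitters, and that half of the other non-remitters transfer. Each of those others is seen for (26 + 56)/2 = 41 weeks on average, so an early exit costs 41 − 8 = 33 weeks. The follow-up gap is then 2.25 − 33x weeks, where x is the excess proportion of early exits on RHB-104. It is zero at x = 2.25/33, about 7 points, and reverses beyond that.

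**The case against.** **The effect is modest and conditional.** This stands. Transfer is optional and its uptake unknown, so the effect may be zero. At 162 per arm, the standard error of a difference between percentages near 35% is √(2 × 0.35 × 0.65/162), about 5.3 points, which is larger than any figure above. No AE hypothesis test is planned. Transfer cannot affect first events before Week 26, so if events occur mainly during titration the distortion is close to nil. Protocol Version 11.0 also times the final analysis at about 324 Week 26 completers. If the safety data were cut then, later follow-up would be shorter in both arms and the effect smaller.

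**The plan already shows unequal follow-up.** This stands in part. The disposition and exposure summaries would reveal it, with reasons, and laboratory and vital-sign results are summarised by visit. They do not correct the AE percentages. Table layouts are in a separate document not available here.

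**Subject-year rates can mislead too.** This also stands. Suppose 30% of each arm have a first event at Week 5 and the rest are followed for 36.8 vs 32.3 weeks. Time at risk per subject is 0.3 × 5 + 0.7 × 36.8 = 27.3 weeks vs 0.3 × 5 + 0.7 × 32.3 = 24.1 weeks. The first-event rates are about 57 vs 65 per 100 subject-years, although the risks are equal. Such a rate cannot be the only remedy.

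**Stronger readings to avoid.** A reader might infer that 79% and 64% will leave, but these are ceilings on eligibility and not forecasts of transfer. A reader might also infer that failed titration will be commoner on RHB-104, or that the tables will on balance make the drug look worse. The documents give no titration-failure rate by arm and support neither inference.

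**Conclusion.** The concern holds in limited form. The AE tables as planned can mix drug effect with length of follow-up, and nothing else in the SAP adjusts for this. From transfer alone, the false RHB-104 excess runs from 0 points through about 1.5 to 2.0 at half uptake to an upper limit of about 2.9 to 4.0 at full uptake. This rests on the design remission rates, equal uptake in both arms, equal constant event rates of 0.5 to 1.0 per year, and follow-up of 26 vs 56 weeks. It concerns only first events after Week 26. Withdrawal for failed titration may add to it or offset it, so the net direction is uncertain. The change is worthwhile because it is cheap; the size alone would not make it essential.

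**What to change.** In SAP 6.5.1 and the 14.3.1 tables:

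1. Add by-arm summaries of TEAEs, SAEs and AEs leading to discontinuation from first dose to the Week 26 visit, and name these as the main between-arm comparison. Transfer is not possible before then. This does not remove any imbalance in early withdrawal, so show the number still observed at Week 26 by arm.
2. State that AE observation in this study ends at the earlier of last contact in this study and first dose in RHB-104-04.
3. For the whole study, add an estimate that allows for unequal follow-up, such as cumulative incidence by time since first dose with censoring at that date. Note that leavers are by definition not in remission, so censoring may be informative.
4. If subject-year rates are also shown, label them as subjects with a first event per 100 subject-years, split them at Week 26, and note that they assume a constant rate within each period.
5. Keep the crude whole-study percentages as supporting tables.

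The cost is a few more programmed tables and a longer safety output. The date of first dose in RHB-104-04 must be available in this trial's database, which the documents do not confirm. If it is not, use last contact in this study. The exit rules themselves need no change.
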